6.5.1. Endpoint Definition/Derivation

6.5.1.1. Derivation of SARS-CoV-2 Infection

SARS-CoV-2 infection will be defined in participants with negative SARS-CoV-2 status pre-booster by either:

- bAb levels against SARS-CoV-2 nucleocapsid protein negative (as measured by *Roche Elecsys*) at Day 1 that becomes positive (as measured by *Roche Elecsys*) post-baseline, OR
- Positive RT-PCR post-baseline.

The date of documented infection will be the earlier of:

- Date of positive post-baseline RT-PCR result, or
- Date of positive serology test result based on bAb specific to SARS-CoV-2 nucleocapsid

The time to the first SARS-CoV-2 infection will be calculated as:

Time to the 1st SARS-CoV-2 infection = Date of the 1st documented infection – Date of randomization + 1.

Cases will be counted starting 14 days after the randomization, i.e., date of documented infection – date of randomization \geq 14.

The incidence of SARS-CoV-2 infection counted starting 14 days after randomization will be summarized by treatment group.

Supportive analyses will summarize incidence of SARS-CoV-2 infection in which a case is counted after randomization, i.e., date of documented infection – date of randomization \geq 0.

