8.5. Randomization

Vaccination group allocation will be performed at the Day 1 visit during Phase A (blinded) as described in [Section 6.2](#). The confirmation for study vaccine administration must be recorded on the Exposure page of the eCRF.

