6.5.1.2. Derivation of Asymptomatic SARS-CoV-2 Infection

The incidence of asymptomatic SARS-CoV-2 infection measured by RT-PCR and/or serology tests obtained at post-baseline visits counted starting 14 days after randomization

in participants with negative SARS-CoV-2 status pre-booster. This is an exploratory endpoint in Part 1 and a secondary endpoint in Part 2.

Asymptomatic SARS-CoV-2 infection is identified by absence of symptoms and infections as detected by RT-PCR or serology tests. Specifically:

- Absence of COVID-19 symptoms +/- 14 days from the positive test below
- AND at least one from below:
 - bAb level against SARS-CoV-2 nucleocapsid protein negative (as measured by Roche Elecsys) at Day 1 that becomes positive (as measured by Roche Elecsys) post-baseline, or
 - Positive RT-PCR test post-baseline (at scheduled or unscheduled/illness visits)

The date of documented asymptomatic infection is the earlier date of positive serology test result based on bAb specific to SARS-CoV-2 nucleocapsid due to infection, or positive RT-PCR at scheduled visits, with absence of symptoms.

The time to the asymptomatic SARS-CoV-2 infection will be calculated as:

Time to the asymptomatic SARS-CoV-2 infection = Date of asymptomatic SARS-CoV-2 infection – Date of randomization + 1.

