9.5. Appendix E Schedule of Events

Table 10 Schedule of Events Part 1

Visit Number		1	2			3	4	5		6	USV
Type of Visit	C	C	SC	SC	SC	C	C	C	SC	C	C
Month Timepoint		M0				M1	M3	M6	M9	M12	Up to M12
Study Visit Day	Screening ¹	D1 (Baseline)	D8	D15	D22	D29	D85	D179	D269	D359/EoS	USV
Window Allowance (Days)	-28		+3	+3	+3	-3/+7	±7	±14	±7	±14	N/A
Days Since Vaccination	-	0	7	14	21	28	84	178	268	358	
ICF, demographics, concomitant medications, medical history ²	X										
Confirm participant meets inclusion and exclusion criteria	X	X									
Physical examination ³	X	X				X	X	X		X	X
Vital signs ⁴	X	X									X
Pregnancy testing ⁵	X	X									
Randomization		X									

Visit Number		1	2			3	4	5		6	USV
Type of Visit	C	C	SC	SC	SC	C	C	C	SC	C	C
Month Timepoint		M0				M1	M3	M6	M9	M12	Up to M12
Study Visit Day	Screening ¹	D1 (Baseline)	D8	D15	D22	D29	D85	D179	D269	D359/EoS	USV
Window Allowance (Days)	-28		+3	+3	+3	-3/+7	±7	±14	±7	±14	N/A
Days Since Vaccination	-	0	7	14	21	28	84	178	268	358	
Dosing											
Study injection (including 15-minute post-dosing observation period)		X									
Surveillance for COVID-19											
Surveillance for COVID-19/Unscheduled visit ⁶	X	X	X	X	X	X	X	X	X	X	X
Nasopharyngeal swab ⁶		X				X	X	X		X	X
Blood for SARS-CoV-2 surveillance		X				X	X	X		X	
eDiary activation for surveillance for COVID-19/Unscheduled visit						X					

Visit Number		1	2			3	4	5		6	USV
Type of Visit	C	C	SC	SC	SC	C	C	C	SC	C	C
Month Timepoint		M0				M1	M3	M6	M9	M12	Up to M12
Study Visit Day	Screening ¹	D1 (Baseline)	D8	D15	D22	D29	D85	D179	D269	D359/EoS	USV
Window Allowance (Days)	-28		+3	+3	+3	-3/+7	±7	±14	±7	±14	N/A
Days Since Vaccination	-	0	7	14	21	28	84	178	268	358	
eDiary prompts every 2 weeks for surveillance for COVID-19 and major changes in health						eDiary prompts every 2 weeks (Day 43 through Day 359/EoS)					
Immunogenicity Assessment											
Blood for humoral immunogenicity ⁷		X				X	X	X		X	

Visit Number		1	2			3	4	5		6	USV
Type of Visit	C	C	SC	SC	SC	C	C	C	SC	C	C
Month Timepoint		M0				M1	M3	M6	M9	M12	Up to M12
Study Visit Day	Screening ¹	D1 (Baseline)	D8	D15	D22	D29	D85	D179	D269	D359/EoS	USV
Window Allowance (Days)	-28		+3	+3	+3	-3/+7	±7	±14	±7	±14	N/A
Days Since Vaccination	-	0	7	14	21	28	84	178	268	358	
Safety Assessments											
eDiary activation for recording solicited adverse reactions (7 days) ⁸		X									
Review of eDiary			X								
Follow-up safety			X	X	X				X		
Recording of Unsolicited AEs		X	X	X	X	X					

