Window Allowance (Days)	-28		+3	+3	+3	-3/+7	±7	±14	±7	±14	N/A
Days Since Vaccination	-	0	7	14	21	28	84	178	268	358	
ICF, demographics, concomitant medications, medical history ²	X										
Confirm participant meets inclusion and exclusion criteria	X	X									
Physical examination ³	X	X	X			X	X	X		X	X
Vital signs ⁴	X	X									X
Pregnancy testing ⁵	X	X									
Randomization		X									
Dosing											

Visit Number		1	2			3	4	5		6	USV
Type of Visit	C	C	C/SC	SC	SC	C	C	C	SC	C	C
Month Timepoint		M0				M1	M3	M6	M9	M12	Up to M12
Study Visit Day	Screening ¹	D1 (Baseline)	D8	D15	D22	D29	D85	D179	D269	D359/EoS	USV
Window Allowance (Days)	-28		+3	+3	+3	-3/+7	±7	±14	±7	±14	N/A
Days Since Vaccination	-	0	7	14	21	28	84	178	268	358	
Study injection (including 15-minute post-dosing observation period)		X									

Visit Number		1	2			3	4	5		6	USV
Type of Visit	C	C	C/SC	SC	SC	C	C	C	SC	C	C
Month Timepoint		M0				M1	M3	M6	M9	M12	Up to M12
Study Visit Day	Screening ¹	D1 (Baseline)	D8	D15	D22	D29	D85	D179	D269	D359/EoS	USV
Window Allowance (Days)	-28		+3	+3	+3	-3/+7	±7	±14	±7	±14	N/A
Days Since Vaccination	-	0	7	14	21	28	84	178	268	358	
Surveillance for COVID-19											
Surveillance for COVID-19/Unscheduled visit ⁶	X	X	X	X	X	X	X	X	X	X	X
Nasopharyngeal swab ⁶		X				X	X	X		X	X
Blood for SARS-CoV-2 surveillance		X				X	X	X		X	
eDiary activation for surveillance for COVID-19/Unscheduled visit						X					
eDiary prompts every 2 weeks for surveillance for COVID-19 and major changes in health						eDiary prompts every 2 weeks (Day 43 through Day 359/EoS)					

Visit Number		1	2			3	4	5		6	USV
Type of Visit	C	C	C/SC	SC	SC	C	C	C	SC	C	C
Month Timepoint		M0				M1	M3	M6	M9	M12	Up to M12
Study Visit Day	Screening ¹	D1 (Baseline)	D8	D15	D22	D29	D85	D179	D269	D359/EoS	USV
Window Allowance (Days)	-28		+3	+3	+3	-3/+7	±7	±14	±7	±14	N/A
Days Since Vaccination	-	0	7	14	21	28	84	178	268	358	
Immunogenicity Assessment											
Blood for humoral immunogenicity ⁷		X				X	X	X		X	
Blood for cellular immunogenicity in a subset of participants ⁷		X	X								
Safety Assessments											
eDiary activation for recording solicited adverse reactions (7 days) ⁸		X									
Review of eDiary			X								
Follow-up safety			X	X	X				X		
Recording of Unsolicited AEs		X	X	X	X	X					

Visit Number		1	2			3	4	5		6	USV
Type of Visit	C	C	C/SC	SC	SC	C	C	C	SC	C	C
Month Timepoint		M0				M1	M3	M6	M9	M12	Up to M12
Study Visit Day	Screening ¹	D1 (Baseline)	D8	D15	D22	D29	D85	D179	D269	D359/EoS	USV

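### Infections detected only by serology are dated at the blood draw, so the 14-day exclusion cannot remove any conversion first seen at Day 29

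*SAP*

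**What the plan says.** SAP 6.5.1.1 applies to participants who are SARS-CoV-2 negative before the booster. It accepts either of two events as infection: nucleocapsid (N) antibody turning from negative at Day 1 to positive, or a positive post-baseline RT-PCR. The documented date is the earlier of the RT-PCR date and the "Date of positive serology test result based on bAb specific to SARS-CoV-2 nucleocapsid". The section then states: "Cases will be counted starting 14 days after the randomization". A supportive analysis counts cases from randomization.

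SAP 6.5.1.2 defines asymptomatic infection as "measured by RT-PCR and/or serology tests obtained at post-baseline visits counted starting 14 days after randomization" and uses the same serology date. It calls this endpoint secondary in Part 2 and exploratory in Part 1.

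In SAP Appendix E, the rows "Blood for SARS-CoV-2 surveillance" and "Nasopharyngeal swab" are marked in both parts at Days 1, 29, 85, 179 and 359. Day 29 has a window of -3/+7 days. Nothing is scheduled in either row between Day 1 and Day 29. The unscheduled-visit column has a swab but no surveillance blood. Protocol 8.5 places randomization at the Day 1 visit.

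**The concern.** A positive N-serology result shows that infection happened at some time since the last negative sample. It does not show when. The SAP assigns the whole interval to its right-hand end. For the first interval, that end always lies beyond the 14-day threshold, so for these cases the exclusion never operates.

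The RT-PCR route only partly compensates. With no scheduled swab between Day 1 and Day 29, an early infection is dated by RT-PCR only if symptoms or a known exposure lead to a test. The eDiary surveillance is activated at Day 29 and its prompts start at Day 43. An early asymptomatic infection without known exposure has no planned RT-PCR route.

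At stake is the relative efficacy estimate for SARS-CoV-2 infection and for asymptomatic infection. The comparison is between two active boosters, so any true difference may be modest and dilution matters more.

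**Working it through.** The documents give no event count, rate or power for these endpoints, so there is no plan figure to reproduce.

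**Inputs from the documents**
- Randomization and dosing are on Day 1, offset 0 (Protocol 8.5; SAP Appendix E).
- The first post-baseline serology draw is Day 29, -3/+7 (SAP Appendix E).
- A case counts if documented date minus randomization date is at least 14 (SAP 6.5.1.1).
- Person-time runs from randomization to the event date or to a censoring date (SAP 6.5.2).

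**Assumptions, not in the documents**
- The infection hazard is constant.
- The lag L from infection to N-positivity is 0 to 14 days.
- The rate ratio is 1 in the first 14 days and 0.70 afterwards (true efficacy 30%).

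**Step 1: does the threshold ever exclude a Day 29 conversion?** The nominal offset is 29 - 1 = 28, the earliest 28 - 3 = 25 and the latest 28 + 7 = 35. All are at least 14, so it never does.

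**Step 2: what share of Day 29 serology-only conversions arose in the excluded window?** With visit offset v, share = min(14, v - L) / (v - L).

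| Lag L (days) | v = 25 | v = 28 | v = 35 |
|---|---|---|---|
| 0 | 56% | 50% | 40% |
| 7 | 78% | 67% | 50% |
| 10 | 93% | 78% | 56% |
| 14 | 100% | 100% | 67% |

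**Step 3: dilution.** If w is the early share of counted cases, observed rate ratio = w × 1 + (1 - w) × 0.70, so observed efficacy = (1 - w) × 30%.

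- Day 29 serology-only conversions alone, nominal visit: w = 50%, 67% and 100% (L = 0, 7, 14) gives rate ratios of 0.85, 0.90 and 1.00.
- All cases serology-only, follow-up to Month 3 (offset 84): w = 14 / (84 - L), from 17% (L = 0) to 20% (L = 14). The rate ratio is 0.75 to 0.76, so efficacy is 25% to 24%.
- Half of infections serology-only, to Month 3, L = 0: 7 early cases are counted and 7 are excluded by their RT-PCR date. Then w = 7 / (7 + 70) = 9%, and efficacy is 27%.
- All cases serology-only, to Day 359 (offset 358), L = 0: w = 14 / 358 = 4%, and efficacy is 28.8%.
- Half serology-only, to Day 359: w = 7 / (7 + 344) = 2%, and efficacy is 29.4%.

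**Step 4: which cases escape?** Under 6.5.1.1, an RT-PCR positive in the first 14 days sets the date and the case is not counted. Under 6.5.1.2, only RT-PCR positives at scheduled visits set the date, so an early unscheduled positive could still be dated at Day 29. Symptomatic COVID-19 (SAP 6.5.1.3) requires RT-PCR and symptoms, so it is untouched.

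**The case against.** The mechanics are hard to dispute, but several points limit their weight.

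- **No rationale is stated.** The 14-day rule is written on the documented date, and the SAP does not say that it is there to remove infections acquired before the booster acts. This stands as a caution about intent. It does not change the fact that, for serology-only cases, the rule does nothing at Day 29.
- **The size rests on assumptions.** The lag, the hazard, the equal early risk and the share of serology-only cases all come from outside the documents. This stands. A reader might infer a much larger effect by taking every counted case as serology-only with follow-up ending at Month 3, or by supposing that around 30% of counted cases are early. The documents do not support that. RT-PCR-detected early cases are excluded under 6.5.1.1, serology continues to Day 359, and nothing gives a 30% share.
- **No formal claim depends on it.** These endpoints carry no hypothesis test or alpha. Protocol 9.6.2 makes efficacy estimation conditional on enough cases, although SAP 6.5 says that it will be estimated. The rule is the same in both arms. A reader might infer a risk of a false superiority finding, but under equal early risk the bias is towards no difference.
- **Some planned output helps.** SAP 6.5 summarizes serology by visit, so Day 29 positives will be visible. The from-randomization analysis drops the exclusion but does not re-date cases. SAP 6.5.3 allows other start times, and one after the Day 29 window would remove these cases. However, that analysis is optional and names no start time. These points mitigate the problem without repairing it.

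**Conclusion.** The concern holds for serology-only infections. Every such conversion first seen at a scheduled Day 29 draw is counted as a case from 14 days onward, whenever infection occurred. This follows from the dating rule and the visit schedule alone.

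The size depends on the assumptions listed. Between 50% and 100% of these conversions at the nominal visit come from the excluded window for lags of 0 to 14 days. If the rate ratio is 1 in that window, an assumed true efficacy of 30% is estimated at roughly 25% in the most affected case (all serology-only, follow-up to Month 3). It is about 29% with follow-up to Day 359, and closer to 30% when many cases are RT-PCR-detected. Censoring at an outside booster, possible after Month 3 in Part 2, puts the realistic value between these. Person-time for the affected cases also runs to the visit date and is somewhat overstated.

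The affected endpoints are SARS-CoV-2 infection and asymptomatic infection, assessed as secondary in Part 2 and exploratory in Part 1. The derivation is worth correcting, but the trial's main conclusions do not rest on it.

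**What to change.** In SAP 6.5.1.1 and 6.5.1.2, for the 14-day analysis:

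- Count a serology-only infection only if an N-negative sample taken at least 14 days after randomization (normally Day 29) precedes the positive one.
- Start at-risk time for serology-only cases at that sample.
- Keep Day 29 conversions, and conversions in participants with no Day 29 sample, in the planned from-randomization supportive analysis, and report their number by arm.

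Dating conversions at the midpoint between samples would not work. The Day 1 to Day 29 midpoint is 28 / 2 = 14 at the nominal visit, which still passes. Across the window it runs from 12.5 to 17.5, so appointment timing would decide which cases count.

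The change is to the derivation and uses data already scheduled for collection. Its cost is the loss of true serology-only infections on Days 14 to 28 from the 14-day count: 50% of Day 29 conversions at zero lag, 33% at a 7-day lag and none at a 14-day lag, under the same assumptions. If the sponsor prefers to keep the current derivation, this version should at least be a pre-specified sensitivity analysis.

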6.5.1.2. Derivation of Asymptomatic SARS-CoV-2 Infection

The incidence of asymptomatic SARS-CoV-2 infection measured by RT-PCR and/or serology tests obtained at post-baseline visits counted starting 14 days after randomization

in participants with negative SARS-CoV-2 status pre-booster. This is an exploratory endpoint in Part 1 and a secondary endpoint in Part 2.

Asymptomatic SARS-CoV-2 infection is identified by absence of symptoms and infections as detected by RT-PCR or serology tests. Specifically:

- Absence of COVID-19 symptoms +/- 14 days from the positive test below
- AND at least one from below:
 - bAb level against SARS-CoV-2 nucleocapsid protein negative (as measured by Roche Elecsys) at Day 1 that becomes positive (as measured by Roche Elecsys) post-baseline, or
 - Positive RT-PCR test post-baseline (at scheduled or unscheduled/illness visits)

The date of documented asymptomatic infection is the earlier date of positive serology test result based on bAb specific to SARS-CoV-2 nucleocapsid due to infection, or positive RT-PCR at scheduled visits, with absence of symptoms.

The time to the asymptomatic SARS-CoV-2 infection will be calculated as:

Time to the asymptomatic SARS-CoV-2 infection = Date of asymptomatic SARS-CoV-2 infection – Date of randomization + 1.

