- Date of the positive RT-PCR test,
- Date of eligible symptom(s), defined as earliest of
 - Systemic symptoms: earliest date of the 2nd eligible systemic symptom is reported
 - Respiratory symptom: earliest date of an eligible respiratory symptom is reported

For the secondary definition of a COVID-19 infection, the date of documented COVID-19 will be the later date of:

- Date of positive RT-PCR test,
- Date of eligible symptom(s), defined as earliest of
 - Respiratory symptom: earliest date of an eligible respiratory symptom is reported
 - Systemic symptoms: earliest date of the eligible systemic symptom is reported

The time to the first occurrence of COVID-19 will be calculated as:

Date of documented Case Definition of COVID-19 – Date of randomization + 1.

Cases will be counted starting 14 days post randomization, i.e., date of documented COVID-19 – Date of randomization \geq 14.

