6.5.2. Analysis Method

The number and percentage of participants who had each type of event (i.e., an asymptomatic or a symptomatic SARS-CoV-2 infection) will be summarized in the PPSE.

As per Phase B, participants are allowed to receive an additional booster outside of the study. Participants who received this additional booster may be censored in the efficacy analyses at the time of booster, as outlined below.

The incidence rate of each type of event will be calculated as the number of cases divided by the total person-time. Person-time is defined as the total time from randomization date to the date of event, last date of study participation, censoring time, date of additional booster outside of the study or efficacy data cutoff date, whichever is earlier.

The 95% CI of the incidence rate will be calculated using the exact method (Poisson distribution) and adjusted by person-time.

Vaccine efficacy and the respective 95% CI will also be estimated.

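### SAP 6.5.1.2 (asymptomatic infection): unscheduled-PCR cases get no date or a late one, the symptom check has no stated anchor when PCR and serology are both positive, and serology-only cases get a 14-day look-back

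*SAP*

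**What the plan says.** SAP 6.5.1.2 states the principle as "Asymptomatic SARS-CoV-2 infection is identified by absence of symptoms and infections as detected by RT-PCR or serology tests". It then sets the operational rule, "Absence of COVID-19 symptoms +/- 14 days from the positive test below", together with at least one of two tests. One is anti-nucleocapsid (anti-N) antibody that is negative at Day 1 and positive later. The other is "Positive RT-PCR test post-baseline (at scheduled or unscheduled/illness visits"). The event date is the earlier of the positive serology date and "positive RT-PCR at scheduled visits, with absence of symptoms". Cases count from 14 days after randomization.

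Three other places matter:

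- SAP 6.5.1.1 dates any SARS-CoV-2 infection from the earlier of PCR and serology. Its PCR limb reads "Date of positive post-baseline RT-PCR result, or" and sets no limit on visit type.
- SAP 6.5.1.3 says of COVID-19: "Cases will be counted starting 14 days post randomization". SAP 6.5.2 needs an event date for every case: "Person-time is defined as the total time from randomization date to the date of event".
- In both schedules of SAP Appendix E, the row "Blood for SARS-CoV-2 surveillance" is marked only at Days 1, 29, 85, 179 and 359, with nothing at unscheduled visits.

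The endpoint is exploratory in Part 1 and secondary in Part 2. SAP 6.5 plans incidence rates and vaccine efficacy with a 95% CI.

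**The concern.** A PCR result fixes an infection closely in time, so a symptom window of 14 days either side suits it. A first positive anti-N draw shows only that infection fell somewhere since the last negative draw, yet the same window is applied.

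The inclusion criterion and the dating sentence, a few lines apart, also use different sets of PCR results. And the phrase about the positive test assumes there is only one, whereas an infected participant can have both a positive PCR and a later positive draw.

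What is at stake is the reproducibility and meaning of this endpoint. Two programmers following the text could reach different counts and different person-time, and some infections with symptoms could be reported as asymptomatic.

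**Working it through.** The documents give no event count, power or expected rate for this endpoint, so there is no figure to reproduce. The check applies the rules to the visit schedule and to worked cases, taking Day 1 as the day of randomization.

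**Share of each between-draw interval that the look-back covers** = 14 / (days between draws), with scheduled days and visit windows from Appendix E.

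| Draw | Interval (days) | Covered | Not covered | Share with visit windows |
|---|---|---|---|---|
| Day 29 | 29 - 1 = 28 | 14/28 = 50.0% | Days 1-14 (14 days) | 14/35 = 40.0% to 14/25 = 56.0% |
| Day 85 | 85 - 29 = 56 | 14/56 = 25.0% | Days 29-70 (42 days) | 14/66 = 21.2% to 14/42 = 33.3% |
| Day 179 | 179 - 85 = 94 | 14/94 = 14.9% | 80 days | 14/115 = 12.2% to 14/73 = 19.2% |
| Day 359 | 359 - 179 = 180 | 14/180 = 7.8% | 166 days | 14/208 = 6.7% to 14/152 = 9.2% |

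Up to Day 85 the look-back covers 14 + 14 = 28 of 84 days (33.3%). The last two rows concern Month 6 and Month 12, whose analyses are exploratory (SAP 6.6).

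**Worked cases**

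1. *Unscheduled PCR positive on Day 40, no symptoms, no seroconversion.* The case meets 6.5.1.2. The dating sentence supplies no date, because the PCR was not at a scheduled visit and there is no positive serology. Neither the 14-day start rule nor person-time can be applied. SAP 6.5.1.1 dates the same infection Day 40. The route is realistic: under protocol 8.9.2 close contact leads to a lateral flow test, and a positive result leads to an illness visit with a swab.
2. *As case 1, but anti-N positive at Day 85.* SAP 6.5.1.2 gives Day 85 and 6.5.1.1 gives Day 40, a shift of 85 - 40 = 45 days.
3. *Cough on Day 39 that resolves before Day 71, unscheduled PCR positive on Day 40, anti-N positive at Day 85.* This is COVID-19, dated Day 40, and it counts because 40 - 1 = 39 is at least 14. If the first positive test anchors the symptom check, or if every positive test must pass it, the case is not asymptomatic. If the Day 85 draw anchors, the symptoms lie outside the window (85 - 14 = 71) and the same infection also counts as asymptomatic. SAP 6.5.1 to 6.5.3 contain no rule that removes it.
4. *Symptoms around Day 45, no positive PCR, anti-N positive at Day 85.* Day 45 is 85 - 45 = 40 days before the draw, so the case is asymptomatic however the anchor is read. Protocol 8.10.4 foresees one such group: symptomatic participants with a positive lateral flow test who are PCR-negative or cannot get a PCR in time.

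The possible double count in case 3 mainly concerns draws from Day 85 on. Before a Day 29 draw the uncovered days are Days 1-14, which precede the start of COVID-19 counting on Day 15, so the effect there is generally misclassification only. A Day 29 visit held on Day 36 would leave Days 15-21 uncovered after that start.

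**The case against.** The strongest counter-argument concerns the look-back. SAP 3.2.1 and protocol Table 4, read literally, attach the absence of symptoms to the PCR limb only; a serology case needs just a negative test at enrollment and a later positive one. On that reading 6.5.1.2 is already stricter than the endpoint, and a longer look-back is a preference. The point stands in part. Both statements are SAP text, so the rule that the SAP prevails over the protocol does not settle it, and 6.5.1.2 states its own principle as absence of symptoms. The two sections must be aligned, and the longer look-back belongs in a sensitivity analysis. Symptoms over 56 days or more are often non-specific, so a full redefinition could wrongly remove truly asymptomatic cases.

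On the anchor, the dating sentence picks the earlier date, which suggests the first positive test. It is not conclusive, because its PCR limb omits unscheduled results. A reader might infer that no anchor is ever named, or that double counting will occur. The text supports neither: with one positive test that test is the anchor, and double counting depends on using the draw when several tests are positive.

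On dating, a reader might infer that unscheduled-PCR cases never receive a date. Those that seroconvert do, at the later draw.

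Protocol 8.9.2 directs symptomatic participants to test within 24 hours and arranges a swab visit after a positive or equivocal result. This narrows the group in case 4 but does not remove it. The lateral-flow sensitivity analyses in SAP 6.5.3 modify the COVID-19 definitions and leave the asymptomatic rule unchanged.

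**Conclusion.** The concern holds within limits. The dating sentence is wrong as written, because it contradicts the criterion in the same section and departs from 6.5.1.1. The missing anchor is a real gap, but only when PCR and serology are both positive. The short look-back is a limitation of serology-only cases: 50% of the time before the Day 29 draw and 25% before the Day 85 draw is checked at nominal visit days.

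Those percentages would be shares of infections only if infection days were spread evenly, which the documents do not show. It would be tempting to read them as misclassification rates, or to conclude that vaccine efficacy is biased in a particular direction. Neither follows: the documents give no attack rate, symptomatic share or seroconversion rate, and the same rule applies in both arms. No alpha is attached to this endpoint. The overall infection endpoint, which 6.5.1.1 derives separately, and the primary immunogenicity analyses are unaffected.

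**What to change.** 1. Date PCR-defined asymptomatic cases from the first post-baseline positive RT-PCR at any visit, scheduled or unscheduled, as 6.5.1.1 already does.
2. State that the symptom check applies to the participant's first positive PCR or anti-N test. Do not count a later seroconversion as asymptomatic when a PCR-confirmed symptomatic infection lies between the last N-negative and first N-positive samples.
3. Keep the window of 14 days either side as the main analysis. Add a sensitivity analysis for serology-only cases that extends the look-back to the last N-negative draw. Use the symptom criteria of SAP Table 6, include lateral-flow-positive episodes without a positive PCR, and exclude solicited post-vaccination reactions.
4. Align SAP 3.2.1 with 6.5.1.2 on whether the serology limb requires absence of symptoms.

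The cost is SAP text and a little more programming, with no new data collection. Symptom data are sparser before the two-weekly eDiary prompts begin on Day 43, and non-specific symptoms may move some truly asymptomatic cases in the sensitivity analysis. Protocol section 9 requires an amendment for changes to secondary objectives or their methods, and lets changes to other secondary or exploratory analyses be listed in the SAP or study report. The sponsor should state which applies and document the change accordingly.
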